18.1.11.2 Assessments of pre-/on-/post-treatment-period

The calculation of the pre-/on-/post-treatment- period will be based on the date information given for IMP administration and for Visit VE (see Section [8.2.2](#)).

18.1.11.3 Assessment of TEAEs

The assessment whether an AE is a TEAE, a pre-treatment or a post-treatment non-TEAE of the different trial periods will be done after replacement of missing date information.

18.1.11.4 Handling different episodes of the same adverse event

Changes in any of the attributes of an ongoing adverse event will be documented by recording a separate episode of the same adverse event. A new episode demands a new entry of start date seriousness, intensity, action taken with IMP and causal relationship to IMP, while AE number, AE term, outcome, countermeasures and end date (or continuing) will be assessed only once for the same AE.

If there are multiple consecutive episodes of one AE starting in the same subject during the same period, these episodes will be analyzed as one (combined) AE with the highest intensity, the worst causal relationship, the worst seriousness, and all actions taken with IMP. Onset of this combined event is the onset of the first event.

In the following causal relationship is ordered in descending order starting with the worst expression:

Expression
1) certain, 2) probable/likely, 3) possible, 4) conditional /unclassified, 5) unassessable/unclassifiable, 6) unlikely, 7) not related

If a non-TEAE worsens after IMP intake, it has to be reported as non-TEAE until worsening and as TEAE afterwards.

If an AE worsens in any attribute in a different trial period, it will be analyzed with the previous attribute as continuing AE for the previous period and the new attribute in the consecutive period.

If an AE improves in any attribute in a different trial period, the above methods for different episodes of the same AE in the same period apply and the AE will be reported as “ongoing” from the previous period as described in Section [15.1.2.1](#).

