14.2.7.1 Adverse events

The original terms used in the CRFs by investigators to identify adverse events will be coded using the most recent version of Medical Dictionary for Regulatory Activities (MedDRA) implemented by the sponsor.

Adverse events will be categorized by seriousness, intensity, outcome, countermeasures, and relationship to IMP and will be tabulated by system organ class and preferred term. Adverse events will be tabulated separately for the treatment periods.

Those TEAEs which started in Treatment Period and are carried over into Tapentadol Period will be considered as ongoing TEAEs. A worsening of a TEAE in Tapentadol Period in a subject previously treated with morphine PR in Treatment Period will be considered as a new TEAE.

The frequency and severity of adverse events will be analyzed descriptively as described in Section [14.2.2](#) both on a subject and event-based level.

All adverse events will be listed. Serious adverse events will be listed separately. Non-TEAEs will be listed separately.

Special attention will be given to those subjects who have discontinued treatment due to an adverse event or who experienced a severe or a serious adverse event. Such cases will be analyzed individually.

Confidential

Protocol KF5503-66
including Amendment 05Page 92 of 137
DMS version 9.0
27 Jul 2017

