7 DOCUMENT AND CHANGE HISTORY

7.1 Changes in analysis compared to the trial protocol

Not applicable.

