15.1.2 Adverse events

Definition of non-treatment emergent adverse events (non-TEAE)

- All adverse events occurring during the pre-treatment Period (defined in Section [8.2.2](#)) are defined as pre-treatment non-TEAEs.
- All adverse events occurring during the post-Treatment Period (defined in Section [8.2.2](#)) are defined as post-treatment non-TEAEs.

Definition of treatment emergent adverse events (TEAE)

- All adverse events occurring or worsening on-treatment in one of the trial periods (defined in Section [8.2.2](#)) are defined as TEAEs of this period. Due to the consideration of the therapeutic reach in the definition of the on-treatment period, a TEAE that occurred during the on-treatment period of the Treatment or Tapentadol Period will be assigned to this trial period, although it actually might have started during the Observation Period.

The assessment whether an AE is a TEAE or a non-TEAE will be based on the start time of the AE recorded on the Adverse Event page of the eCRF. In case of partial dates or times, this assessment is done after imputation of missing date/time information; an AE will be considered treatment emergent unless the information available will clearly exclude it. For details on the imputation of missing date/time and programming aspects of adverse events in general, see Section [18.1.11](#).

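### The SAP makes a carried-over AE that worsens in any attribute, causality included, a Tapentadol Period TEAE whatever the Part 1 drug; the protocol names this only after morphine, and SAP 7.1 declares no change

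*SAP*

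**What the plan says.** SAP 18.1.11.4 lists what is recorded afresh when an ongoing event changes: "A new episode demands a new entry of start date seriousness, intensity, action taken with IMP and causal relationship to IMP". Consecutive episodes starting in the same period are merged into one event that carries the highest intensity and the worst causality and seriousness. Across periods the treatment differs: "If an AE worsens in any attribute in a different trial period, it will be analyzed with the previous attribute as continuing AE" for the earlier period, and the new attribute goes to the next. For improvement the text begins "If an AE improves in any attribute in a different trial period, the above methods for different episodes of the same AE" and ends with the event being reported as ongoing from the earlier period.

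Causality is given a direction. The SAP introduces its list with "In the following causal relationship is ordered in descending order starting with the worst expression" and runs from certain down to not related. No order is given for action taken with IMP.

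SAP 15.1.2 defines the TEAEs of a period as "All adverse events occurring or worsening on-treatment in one of the trial periods", without reference to Part 1 treatment.

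Protocol 14.2.7.1 states: "Those TEAEs which started in Treatment Period and are carried over into Tapentadol Period will be considered as ongoing TEAEs". Its next sentence says that "A worsening of a TEAE in Tapentadol Period in a subject previously treated with morphine PR in Treatment Period" is to be taken as a new TEAE. It has no matching sentence for children who took tapentadol in Part 1.

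SAP 7.1, which should list changes in analysis from the protocol, reads "Not applicable".

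**The concern.** There are two departures, and neither is declared.

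First, the protocol's worsening rule depends on the Part 1 drug and the SAP's does not. The protocol gives no reason for its distinction, but there is a plausible one. Under protocol 10.2.3.3, tapentadol-pretreated children continue on their last Part 1 dose, so for them the period boundary is administrative. Morphine-pretreated children change drug there.

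Second, the SAP's trigger is wider than clinical worsening. A change in the investigator's causality opinion is enough, even if nothing has changed in the child. Within one period the same change would simply be merged into a single event.

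Tolerability, measured by number and type of adverse events per period at subject and event level, is a main secondary endpoint (protocol 8.1.2, SAP 15.1). Long-term safety is the objective of Part 2. An event assigned again to the Tapentadol Period enters its incidence and event counts (SAP 15.1.2.2). In the exposure-adjusted rate (SAP 15.1.2.3) it adds to the numerator and also ends that child's time at risk.

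**Working it through.** **How a carried-over event becomes a TEAE.** The cross-period sentence in SAP 18.1.11.4 does not itself use the word TEAE. The count follows in two steps. That sentence places the worsened attribute in the later period. SAP 15.1.2 then makes an event that worsens on treatment in a period a TEAE of that period. The improvement rule supports this reading, because 18.1.11.4 sends improved events, and not worsened ones, to the ongoing category.

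**The rules side by side, for an event carried into the Tapentadol Period.**

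| Change in the event | Part 1 drug | Protocol 14.2.7.1 | SAP 18.1.11.4 with 15.1.2 |
|---|---|---|---|
| None, or improved | Either | Ongoing | Ongoing from Part 1 (row in 15.1.2.1) |
| Intensity or seriousness increases | Morphine | New TEAE | TEAE of the period |
| Intensity or seriousness increases | Tapentadol | Ongoing by the general rule; worsening not mentioned | TEAE of the period |
| Causality only, re-rated upward | Morphine | Unclear: worsening not defined there | TEAE of the period |
| Causality only, re-rated upward | Tapentadol | Ongoing by the general rule | TEAE of the period |
| Action taken only | Either | Not addressed | Undetermined: no order given |

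**Causality.** The SAP ranks are certain 1, probable/likely 2, possible 3, conditional/unclassified 4, unassessable/unclassifiable 5, unlikely 6, not related 7. Unlikely to possible moves from 6 to 3 and so is a worsening. Conditional to possible moves from 4 to 3 and is also a worsening, although protocol 12.6.1 uses conditional for an assessment that is still waiting for data. Completing a pending assessment can therefore meet the rule.

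**Size.** The plan gives no figure to reproduce. The number n of tapentadol-pretreated children entering the Tapentadol Period is not stated, so it is assumed. The number allocated to tapentadol at the planned 2:1 ratio is 69 × 2/3 = 46. With k re-counted children on one preferred term, the crude incidence rate rises by 100 × k/n percentage points. The preferred-term and exposure-adjusted tables show terms at 5% or more, so from zero the smallest k that qualifies satisfies k/n ≥ 0.05.

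| n | Rise for k = 1 (points) | Smallest k for 5% |
|---|---|---|
| 10 | 10.0 | 1 |
| 15 | 6.7 | 1 |
| 20 | 5.0 | 1 |
| 30 | 3.3 | 2 |
| 46 | 2.2 | 3 |

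These figures show sensitivity per child. They do not estimate how many children would be affected.

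**The case against.** The strongest reply is that the SAP rule is a reasonable, symmetric and cautious choice. Protocol 14.2 leaves analysis detail to the SAP. Protocol 12.6.1 already counts pre-treatment events that worsen on treatment as TEAEs and requires a separate episode for a change in any attribute. Protocol 14.2.7.1 neither says *only* after morphine nor defines worsening. Safety analyses are descriptive, without tests between arms (SAP 15), and the primary endpoint is untouched.

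Much of this stands. The protocol's restriction is inferred from a general rule followed by one named case. The breadth of attributes extends undefined text and does not contradict a definition. Counting true worsening in both pretreatment groups is defensible. What the reply does not answer is that the SAP differs from the protocol's stated treatment of carried-over events while declaring no difference, and that its trigger takes in causality re-ratings.

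Three stronger readings are tempting and are not supported:

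- A reader might infer that opioid effects that began in Part 1 are generally counted again. They are not: unchanged and improved events have their own ongoing row at subject and event level (SAP 15.1.2.1).
- A reader might infer that routine titration triggers re-counting through action taken. With no order defined, an action cannot clearly worsen, so this is an ambiguity only.
- A reader might infer that terms will be pushed into the safety tables. The documents give no carry-over or re-rating rate. At n above 20, two or more children would have to share a term otherwise absent in that arm. The tables by system organ class and preferred term have no 5% limit, so no term depends on this rule to be reported there.

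**Conclusion.** The point holds as an undeclared difference between SAP and protocol, together with a trigger that is too wide. Under the SAP, a carried-over event that worsens in any attribute becomes a Tapentadol Period TEAE regardless of Part 1 treatment, and a causality re-rating without clinical change can be enough. For action taken the rule is ambiguous.

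This rests on reading SAP 18.1.11.4 together with 15.1.2, and on taking the protocol's morphine sentence as an exception to its general rule. The total effect cannot be derived from the documents. Per affected child it is 5.0 percentage points on a term at an assumed n of 20 and 2.2 at n = 46. It concerns a descriptive main secondary endpoint and is worth correcting because the correction is cheap.

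**What to change.** In SAP 18.1.11.4, let only an increase in intensity or seriousness make a carried-over event a TEAE of the next period. Show changes in causality and action taken in listings.

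Then reconcile the SAP with protocol 14.2.7.1 in one of two ways:

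- apply the protocol's restriction of new TEAEs on worsening to morphine-pretreated subjects; or
- count worsening in both pretreatment groups and record this in SAP 7.1 as a change from the protocol.

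The first option should not be taken by default, because a true worsening on long-term tapentadol would then not count as a Part 2 TEAE. Under either option, show worsened carried-over events in a row separate from first-onset events, so that neither hides the other.

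The cost is SAP wording, one programming condition and one extra table row. Tapentadol Period event counts would be slightly lower.

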18.1.11.5 Causal relationship of TEAEs to IMP

The causal relationship of TEAEs to IMP is categorized as follows:

Category	Assessment by investigator:
related	certain probable / likely possible
not related	unlikely not related
unknown	unassessable/ unclassifiable conditional /unclassified causal relationship is missing

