8.1.2 Secondary endpoint definitions

The main secondary endpoints are:

Part 1

- Constipation as assessed by changes from baseline (Visit V2) of total scores for the modified CAS.

Part 1 and Part 2

- Tolerability as assessed by the number and type of adverse events and adverse drug reactions by treatment group during the different trial periods, on a subject and event level.

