All TEAEs judged by either the reporting investigator or the sponsor as having a reasonable causal relationship to a medicinal product qualify as adverse drug reactions. The expression "reasonable causal relationship" means to convey, in general, that there is evidence or argument to suggest a causal relationship. For guidance on the causal relationship, see the section [Classification of causation](#).

A list of adverse drug reactions seen for the IMPs are given in the current version of the investigator's brochure for tapentadol PR and in the summary of product characteristics for morphine PR.

Confidential

 Protocol KF5503-66
 including Amendment 05

 Page 76 of 137
 DMS version 9.0
 27 Jul 2017

Classification of causation

The causal relationship of an adverse event to IMP will be classified using the following terminology. The given criteria for each term are for consideration and are neither exhaustive nor required to be fulfilled in total for the selection of the respective term:

Terms for classification of causation	Criteria for the selection of causality classification terms
Conditional/ Unclassified:	Additional data for a proper assessment are under examination.
Unassessable/ Unclassifiable:	The available data cannot be judged because information is insufficient or contradictory, and cannot be supplemented or verified.
Not related:	Data with sufficient evidence to accept that there is no causal relationship to IMP administration (i.e., there is no temporal relationship to IMP administration or proved other cause).
Unlikely:	Data without sufficient evidence to accept that there is no causal relationship to IMP administration, but also with no evidence or argument to suggest a causal relationship (e.g., the temporal relationship to IMP administration makes a causal relationship improbable and other drugs, chemicals, or underlying disease(s) provide plausible explanations).
Possible:	Data with limited evidence or argument to suggest a causal relationship (e.g., there is a reasonable time sequence to administration of the drug, but the adverse event could also be explained by concurrent disease[s] or other drugs or chemicals. Information on drug withdrawal may be lacking or unclear).

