15.1 Secondary endpoint

The main secondary endpoints are:

Part 1

Constipation as assessed by changes from baseline of total scores for the modified constipation assessment scale (mCAS).

Part 1 and Part 2

Tolerability as assessed by the number and type of adverse events and adverse drug reactions by treatment arm during the different trial periods, on a subject and event level.

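### The SAP's stand-in for adverse drug reactions uses the investigator's causality judgement alone, while the protocol also counts the sponsor's, so a component of a main secondary endpoint can be reported too low

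*SAP*

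**What the plan says.** Both documents name ADRs in the tolerability endpoint. Protocol Section 8.1.2 has "Tolerability as assessed by the number and type of adverse events and adverse drug reactions by treatment group during the different trial periods", and SAP Section 15.1 repeats it with arm in place of group. Both ask for results by subject and by event.

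Protocol Section 12.6.1 defines the term: "TEAEs judged by either the reporting investigator or the sponsor as having a reasonable causal relationship to a medicinal product qualify as adverse drug reactions". It explains a reasonable causal relationship as meaning, in general, that "there is evidence or argument to suggest a causal relationship". In the same section, under the procedures for serious adverse events, possible or higher is the cut for related.

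The SAP gives no ADR definition and labels no table as ADR. Sections 15.1.2.1 and 15.1.2.2 plan rows and tables for related TEAEs and related serious TEAEs. Section 18.1.11.5 ("The causal relationship of TEAEs to IMP is categorized as follows") derives three categories from the investigator's entry:

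- related: certain, probable/likely, possible;
- not related: unlikely, not related;
- unknown: unassessable, conditional, or no entry.

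No sponsor causality variable appears anywhere in the SAP. Section 7.1, on changes from the protocol, reads as not applicable.

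**The concern.** A main secondary endpoint has a component defined in one document and tabulated under a narrower rule in the other, with no statement that the rule changed. An event that the sponsor judged related and the investigator did not is an ADR under the protocol. In the SAP tables it would fall under not related or unknown.

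The safety analysis is descriptive, so the counts are themselves the result. In arms this small, one event can move the related serious TEAE row from none to one. A reader of the trial report would take the related-TEAE rows as the ADR endpoint, because nothing else in the SAP answers to that name.

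**Working it through.** The documents give no figure for this point, so there is nothing to reproduce. The check compares the two definitions, then illustrates the scale.

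**Definitions side by side**

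| Element | Protocol 12.6.1 | SAP 15.1.2 and 18.1.11.5 |
|---|---|---|
| Whose assessment counts | Investigator or sponsor | Investigator |
| Threshold | Evidence or argument for causality; related means possible or higher | Possible or higher |
| Unassessable causality | Data that cannot be judged | Own category, unknown |
| Output name | Adverse drug reaction | Related TEAE |

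The threshold agrees. The handling of unassessable causality is compatible. The source of the causality assessment differs.

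**Direction**

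Let I be the TEAEs the investigator rates certain, probable/likely or possible, and S those the sponsor judges related.

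- Protocol ADRs = I ∪ S.
- SAP related TEAEs = I.
- Shortfall = events in S but not in I, which is zero or more.

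The shortfall is zero if the sponsor never upgrades an event. The same holds when subjects are counted instead of events.

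**Scale**

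The planned 69 subjects split 2:1 give 46 on tapentadol and 23 on morphine. One child is 1/46 = 2.2 percentage points or 1/23 = 4.3 percentage points.

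For illustration only, let p be the share of subjects with an investigator-related TEAE, and u the share of the remaining subjects who have a TEAE that only the sponsor judges related. Neither value is in the documents. Subjects with an ADR = N × (p + (1 − p) × u). With p = 40% assumed:

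| u | N = 46 | Shortfall | N = 23 | Shortfall |
|---|---|---|---|---|
| 0% | 18.4 | 0 | 9.2 | 0 |
| 5% | 19.8 | 1.4 | 9.9 | 0.7 |
| 10% | 21.2 | 2.8 | 10.6 | 1.4 |
| 20% | 23.9 | 5.5 | 12.0 | 2.8 |

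For example, with u = 5%, 46 × (0.40 + 0.60 × 0.05) = 46 × 0.43 = 19.8. The table shows what sponsor upgrades would do to the counts. It does not predict how often they occur.

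**The case against.** The strongest reply is that no under-count has been shown. It needs sponsor upgrades, and the documents do not show that these occur or that a sponsor causality variable exists. The CRF has one causality item, and the serious adverse event report carries the investigator's assessment. Protocol Section 14.2.7.1 asks only for categorisation by relationship to IMP, which the SAP does. No safety tests are planned (SAP Section 15). All TEAEs and serious TEAEs are tabulated whatever their causality, and Protocol Section 14.2.7.1 has severe and serious cases analysed individually, so a serious event cannot vanish through a causality code.

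Most of that stands, and it limits the size of the point. It does not remove the mismatch. The protocol's definition gives the sponsor's judgement a route to ADR status, the SAP omits it, and Section 7.1 is silent. Nor is a sponsor judgement foreign to these tables: the protocol has the sponsor assess expectedness, and SAP Section 15.1.2.1 tabulates unexpected TEAEs.

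A reader might infer two stronger points.

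- **That unassessable, conditional and missing causality is lost or wrongly excluded.** SAP Section 15.1.2.2 tabulates it as unknown by System Organ Class (SOC) and Preferred Term (PT), and Section 18.1.11.4 ranks conditional and unassessable above unlikely when episodes are combined. Keeping unassessable events out of related fits the protocol, which describes them thus: "The available data cannot be judged because information is insufficient or contradictory, and cannot be supplemented or verified". Counting such events as ADRs would itself depart from the protocol's definition. The remaining gap is small: the unknown category is specified only in event-level tables, so the number of subjects affected is not shown.
- **That open-label investigators attribute opioid effects more readily to morphine, and the sponsor corrects for it.** Nothing in the documents supports such a tilt. Nor do they present the sponsor, which makes the test drug, as a neutral check.

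**Conclusion.** The mismatch is real and undeclared. Under the SAP as written, the ADR component can be reported below the protocol-defined count and never above it. It would be wrong to say that the endpoint *is* under-counted: the shortfall depends entirely on how often the sponsor alone judges an event related, which the documents do not give, and it may be zero. Only the ADR component is affected. Total and serious adverse event counts, the primary endpoint and all error rates are unchanged.

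The conclusion assumes that the related TEAE is meant to stand for the ADR. The SAP does not say so, but it offers nothing else. The correction is worth making before database lock because it brings the SAP into line with the protocol at little cost.

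**What to change.** In SAP Sections 15.1.2 and 18.1.11.5:

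1. Define an ADR as a TEAE that the investigator rates certain, probable/likely or possible, or that the sponsor judges related.
2. Name the source of the sponsor's assessment and the events for which it exists, serious events as a minimum. If it covers only some events, say so in the table footnotes, so that the mixed source is visible.
3. Report ADR rows by subject, event, SOC and PT beside the investigator-related rows.
4. Leave conditional, unassessable and missing causality in unknown, and add one subject-level sensitivity row counting unknown as related.

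If the sponsor's assessment will not be used, Section 7.1 should instead declare that ADRs are reported on the investigator's judgement alone. That would make the departure visible but would not deliver the protocol's definition.

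The cost is SAP wording, a merge of the sponsor assessments that exist, and a few extra table rows. The reported ADR count may be slightly higher. The documents describe no sponsor causality field, so its availability should be confirmed before the text is fixed.
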